9.3 Adverse Events of Special Interests

AEs of special interest will be queried of participants while hospitalized on a daily basis.

9.4 Serious Adverse Event

AEs are classified as serious or non-serious. A *Serious adverse event* is:

- fatal
- life-threatening
- requires re-hospitalization (after hospital discharge for the initial, pre-existing meningitis)
- prolonged hospitalization (due to a new AE; not due to pre-existing meningitis or HIV/AIDS)
- results in persistent or significant disability or incapacity
- results in congenital anomaly or birth defect
- an important medical event that may jeopardize the subject or may require immediate intervention to prevent one of the other outcomes listed in the definition above (e.g., anaphylaxis)

All AEs that do not meet any of the criteria for serious will be classified as *non-serious adverse events*. A standard medical problem, e.g., malaria, which in theory if untreated could result in a fatal or life-threatening event, is not by itself a SAE. If the AE is of sufficient severity to result in hospitalization, then the AE is a SAE.

Routine outpatient medical therapy for a common, expected illness in the study population (e.g., malaria, TB) is not a SAE.

All SAEs will be:

- recorded on the appropriate AE CRF
- followed through resolution by a study clinician
- reviewed and evaluated by a study clinician

Important medical events that may not result in death, be life-threatening, or require hospitalization may be considered an SAE when, based upon appropriate medical judgment, they may jeopardize the patient and may require medical or surgical intervention to prevent one of the outcomes listed above. Examples of such medical events include allergic bronchospasm requiring intensive treatment in an emergency room or at home, blood dyscrasias or convulsions that do not result in inpatient hospitalizations, or the development of drug dependency.

Death due to pre-existing cryptococcal meningitis is not a SAE. Death due to a complication of meningitis (e.g., new seizure) would be a SAE.

Prolongation of hospitalization must be due to a new AE, not the pre-existing cryptococcal meningitis or pre-existing HIV/AIDS and related conditions. A *new* AE must cause the prolonged hospitalization for this to be considered a SAE. Hospitalizations due to cryptococcal meningitis commonly may last 2-4 weeks.

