9.1 Adverse Event (AE) Definitions

The intervention during this trial is the reduced dose of flucytosine for induction therapy.

Adverse Event (AE)

An AE is any untoward medical occurrence in a clinical investigation subject administered a pharmaceutical product and which does not necessarily have to have a causal relationship with this treatment. An AE can therefore be any unfavorable or unintended sign (including abnormal laboratory findings), symptom, or disease temporally associated with the use of a medicinal product. Any symptom, sign, illness or experience that develops or worsens in severity during the course of the study are considered AEs.

Any medical condition already present at the time of screening should not be reported as an adverse event unless the medical condition or signs or symptoms present at baseline changes in severity or seriousness at any time during the study. In this case, it should be reported as an adverse event.

As a diagnosis may have multiple signs or symptoms associated with the AE (e.g., sepsis presenting with fever, hypotension, confusion), a single diagnosis for the AE is preferred over reporting each individual symptom.

Clinically significant abnormal laboratory or other examination (e.g., ECG) findings that are detected during the study or are present at the time of screening and significantly worsen during the study are defined and should be reported as adverse events. The Investigator will exercise his or her medical and scientific judgment in deciding whether an abnormal laboratory finding, or other abnormal assessment is clinically significant. Clinically significant abnormal laboratory values occurring during the clinical study will be followed until repeat tests return to normal, stabilize, or are no longer clinically significant. Any abnormal test that is determined to be an error does not require reporting as an adverse event. Laboratory abnormalities will be separately categorized from clinical AEs.

Worsening of the index indication (cryptococcal meningitis) due to insufficient therapeutic effect of study drug is captured as an efficacy measure (i.e., death, poor early fungicidal activity) and in general will not be considered an adverse event but are captured in other individual trial endpoints. As participants enter the trial with Grade 4 cryptococcal meningitis, worsening is not possible, unless death occurs.

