9.2.1 Severity of Adverse Events

The term severity is defined as the intensity grade or level for a specific event, i.e., mild, moderate, severe, or life-threatening. Importantly, severity is *not* the same as seriousness, which is based on participant/event *outcome or action* criteria usually associated with events that pose a threat to a subject's life or functioning (ICH E2A). The *Division of AIDS (DAIDS) Table for Grading the Severity of Adult and Pediatric Adverse Events (v2.1, July 2017)* will be used. Laboratory AEs will be defined using the statistical database by DAIDS Table grading thresholds.

The Investigator will assess the severity (intensity) of each adverse event as mild, moderate, severe, or life threatening and will also categorize each adverse event as to its potential relationship to study drug using the categories of yes or no.

Assessment of severity:

The severity of all adverse events should be graded as per The *Division of AIDS (DAIDS) Table for Grading the Severity of Adult and Pediatric Adverse Events (v2.1, July 2017 or*

most current). For those adverse events not listed, the following grading system should be used:

- Mild (Grade 1): Transient symptoms, awareness of sign/symptom, but easily tolerated and no interference with patient's daily activities.
- Moderate (Grade 2): Marked signs/symptoms that interfere with a patient's usual activities, but still acceptable.
- Severe (Grade 3): Incapacitating signs/symptoms which cause considerable interference with the patient's daily activities, unacceptable.
- Life-threatening (Grade 4): Life-threatening or disabling adverse event.
- Death (Grade 5): Death-related adverse event.
 - Death from pre-existing cryptococcal infection is part of the survival endpoint, which is expected to be up to 20% of enrolled subjects. Cryptococcal meningitis deaths without other AEs should not be additionally reported as a Grade 5 AE. The objective is to discern Grade 5 deaths due to adverse events versus deaths from the progression of the pre-existing cryptococcal meningitis. Overall survival will be separately analyzed as the secondary endpoint.

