9.2.2 Causality of Adverse Events

The probable causality of the investigational study drug being related to the AE will be collected.

Definitely related	There is a certainty that the AE is related to the study drug.
Probably related	There is a high likelihood that the AE is related to the study drug.
Possibly related	There is a likelihood that the study drug is the cause of the AE, but other causes cannot be ruled out.
Unlikely to be related	It is not likely that the AE is related to the study drug, and other more likely causes are present.
Unrelated	Evidence exists that the AE is related to something other than the study drug.

AEs will use pre-defined causality for the common, expected medical conditions associated with HIV/AIDS (e.g., TB, new opportunistic infections), other infections (e.g., malaria, pneumonia) and cryptococcal meningitis complications. Refer to Manual of Operations for details.

Therapeutic failure of the antifungal therapy alone is not deemed as causal for an AE (i.e. it is unrelated).

The most common disease-related complications and/or standard of care treatment-related side effects include:

- Death due to pre-existing cryptococcosis (up to 20% of enrolled subjects);
- Meningitis complications: e.g., seizures, cranial nerve palsies, increased intracranial pressure
- Transient renal insufficiency in the first 14 days after study entry due to IV amphotericin (20%);
- Cryptococcal IRIS events (~20%);
- AIDS-related opportunistic infections;
- Hospitalization or death due to immune reconstitution inflammatory syndrome (IRIS), cryptococcal culture-positive relapse, or AIDS opportunistic infection (20-25%);^{18,19,26}
- Common ART or flucytosine side effects (e.g., anemia, leukopenia)
- Common IV amphotericin side effects (e.g., anemia, hypokalemia, renal failure)
- Hospital nosocomial infections and other complications (e.g., aspiration pneumonia)

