10.3 Data and Safety Monitoring Board (DSMB) Safety Reviews

Refer to the DSMB Charter for full details.

- DSMB safety reviews will occur after 10 participants have been enrolled and have accrued approximately 2 weeks of follow-up data.

The DSMB committee will consist of [name] as the chairperson, [name], [name], [name], and [name]. The trial PIs and statistician will present to the DSMB in an open session before the DSMB enters into a closed, private session. A quorum of three members will be required to meet, including the DSMB statistician. A local Ugandan community member will be invited to attend open DSMB meetings. The PhD study biostatistician will prepare summary progress reports on tolerability, safety, and efficacy within approximately 30 days of 10 participants being enrolled and accruing 2 weeks of follow up data. At time of the safety reviews, all available data will be utilized, particularly with respect to control subjects.

Data are unblinded, thus the PI, on-site investigators, and other team members will additionally monitor for any unexpected concern. If concerns are raised, this will prompt an unscheduled DSMB safety evaluation.

If there are unexpected safety concerns of serious and potentially related AEs, these AEs will be reviewed by the DSMB, and reported to the relevant regulatory authorities with oversight. Unexpected safety concerns may result in suspension of further trial interventions or closure to further enrollment. The study PIs, DSMB chair, and sponsor each retain the authority to suspend additional enrollment and study interventions for the entire study; however, consensus agreement will be sought. Examples of findings that might trigger a safety review are the number of SAEs overall, the number of occurrences of a particular type of SAE, severe AEs/reactions, or increased frequency of events. In particular, the investigators will be monitoring for culture positive Cryptococcal relapse. This has been rare in previous trials and a small number of cases would be cause for an early safety review. The biostatistician will perform a formal analysis as per the statistical plan.

Reporting to the IRB of record will occur with annual reporting, and after each DSMB report. We will report all deaths, including cryptococcal related deaths to the IRB.

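### In a dose-reduction trial, meningitis deaths stay out of the SAE and Grade 5 counts and no all-cause death trigger is stated; the EFA and relapse triggers fill the gap only in part

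*Combined protocol and SAP*

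**What the plan says.** Four rules in section 9 deal with a death or deterioration attributed to the meningitis itself:

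- Section 9.1: worsening through insufficient effect of the study drug "is captured as an efficacy measure (i.e., death, poor early fungicidal activity") and is generally not an AE.
- Section 9.2.1: "Cryptococcal meningitis deaths without other AEs should not be additionally reported as a Grade 5 AE". Such deaths belong to the survival endpoint, "which is expected to be up to 20% of enrolled subjects".
- Section 9.2.2: "Therapeutic failure of the antifungal therapy alone is not deemed as causal for an AE (i.e. it is unrelated").
- Section 9.4: "Death due to pre-existing cryptococcal meningitis is not a SAE", although a fatal outcome is the first SAE criterion in that section. In contrast, "Death due to a complication of meningitis (e.g., new seizure) would be a SAE".

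Section 9.5 applies its 72-hour clock to SAEs. Section 10.3 schedules a DSMB review after 10 participants have about two weeks of data. On unscheduled reviews it says: "Examples of findings that might trigger a safety review are the number of SAEs overall", followed by counts of a particular SAE type, severe AEs and rising event frequency. On culture-positive relapse it adds: "This has been rare in previous trials and a small number of cases would be cause for an early safety review". Any concern raised from the unblinded data also prompts an unscheduled DSMB evaluation. All deaths go to the IRB, and full details are left to a DSMB charter.

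The synopsis (Phase II Safety Analysis) calls an early DMC if there is statistical evidence that EFA is below 0.2 log10 CFU/mL/day. Section 2.6.1 suspends the trial pending interim review if EFA is consistently below 0.2 after 10 enrolled patients.

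**The concern.** Keeping disease deaths out of the SAE stream is a reasonable convention when the hazard under study is drug toxicity. Here the hazard is loss of effect. If the lower dose fails, the expected result is a death attributed to cryptococcal meningitis, and sections 9.1 to 9.4 place that death outside the AE, SAE, Grade 5 and relatedness counts. The unrelated rule also settles in advance a question that the trial exists to ask.

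At stake is how quickly an excess of deaths would reach the DSMB. After the review at 10 participants, enrolment may run to 50, so up to 50 − 10 = 40 more people could be treated before another review that the protocol schedules.

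**Working it through.** The plan gives no figure for this point, so the check sets the rules side by side and then illustrates two triggers.

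**1. Where a pure meningitis death is counted**

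| Route | Counted? | Section |
|---|---|---|
| AE for insufficient effect | Generally no | 9.1 |
| Grade 5 AE | No | 9.2.1 |
| Related to study drug | Pre-set as unrelated | 9.2.2 |
| SAE, and so 72-hour report | No | 9.4, 9.5 |
| 2-week AE/SAE summaries | No | 11.6 |
| 18-week survival and DOOR | Yes, in the final analysis | 11.5 |
| Report to IRB | Yes; no timing in that sentence, and the one before it puts IRB reporting annually and after each DSMB report | 10.3 |

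**2. Triggers that do not depend on SAE status**

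- EFA: section 2.5 says that people who die rapidly may have no EFA, since at least two time points are needed. Section 2.2 puts about half of the mortality in the first two weeks.
- Relapse: it can be seen only in participants who live long enough to relapse.
- Concern raised: discretionary, with no threshold.

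**3. How much the EFA wording matters**

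Inputs: n = 10 with a calculable EFA (synopsis), SD 0.20 (section 11.4.1), two-sided alpha 0.05 (section 11.1). SE = 0.20/√10 = 0.063.

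- Read as a point estimate below 0.2, P = Φ((0.2 − true)/SE): 0.94 at true EFA 0.10, 0.79 at 0.15, 0.50 at 0.20, 0.06 at 0.30.
- Read as an upper 95% limit below 0.2, the observed mean must be below 0.2 − 2.262 × 0.063 = 0.057. The noncentral t (9 df) then gives 0.29 at true EFA 0.10, 0.11 at 0.15 and 0.025 at 0.20.
- Over assumed SDs of 0.13 to 0.25, the probability at true EFA 0.10 is 0.90 to 0.99 on the first reading and 0.20 to 0.58 on the second.

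The trigger can fire, but its sensitivity at 10 participants depends on a definition that the protocol does not give. Sensitivity to a true EFA below 0.2 rises as more EFAs accrue.

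**4. What a death count could show**

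Reference rates in the documents: 18/222 = 8.1% at two weeks for GCS 15 (Table 2.2; its interval of 4.5% to 11.7% reproduces as a Wald interval), up to 20% with no horizon (sections 9.2.1 and 9.2.2), and 24% at 10 weeks for the best ACTA regimen (section 2.3). The 25% below is an assumed rate. Binomial upper tails:

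| True rate | P(≥3 of 10) | P(≥8 of 40) |
|---|---|---|
| 8.1% | 0.041 | 0.014 |
| 20% | 0.32 | 0.56 |
| 25% | 0.47 | 0.82 |

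At 20% the expected number in 40 is 8, so a threshold of 8 would be reached more often than not with no excess at all.

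**The case against.** A reader might infer that harm from under-dosing cannot set off any listed safety trigger. The documents do not support that. The EFA and relapse triggers target loss of efficacy and ignore SAE status and relatedness. Section 10.3 lists examples only, lets any concern prompt a DSMB evaluation, and has the statistician's report at 10 participants cover efficacy, which under section 9.1 includes death. Deaths from complications of meningitis remain SAEs, and section 9.9 counts new seizures, aspiration pneumonia and hydrocephalus as complications, so part of an excess would register in the SAE counts.

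A reader might also infer that a simple death count would reliably expose a tripling of mortality from 8.1%. That does not hold either: 8.1% is for GCS 15, whereas sections 5.3.3 and 5.3.4 admit participants with GCS below 15 by surrogate consent.

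Two further points are fair. The separation of disease deaths from AE deaths is deliberate, its aim is stated in section 9.2.1, and survival is analysed in its own right. The DSMB charter is not among the documents and may already hold a mortality rule.

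These points limit the finding but do not remove it. Separate tabulation does not require slower reporting or a preset causality call. Sending deaths to the IRB is not the same as sending them to the DSMB. The remaining triggers are discretionary, undefined or blind to early deaths.

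**Conclusion.** The concern holds in this form: deaths attributed to pre-existing meningitis are outside the SAE and Grade 5 counts and the 72-hour reporting, therapeutic failure is unrelated by rule, and the protocol states no all-cause mortality trigger. The EFA, relapse and general-concern triggers cover part of the gap.

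The exposure is up to 40 participants enrolled after the only scheduled DSMB review named. The conclusion rests on the protocol text and assumes that the charter does not already supply a mortality rule. The EFA and binomial probabilities are illustrations under stated assumptions. They show that the EFA wording and the reference death rate both have to be fixed; they do not establish a particular threshold.

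**What to change.** 1. Sections 9.4 to 9.6: report every death, whatever its attributed cause, to the IRB and the DSMB chair on the SAE timeline. Keep disease deaths and AE deaths separate in the tables. State the period covered, because section 9.5 stops at 2 weeks while section 7.4.1 ends expedited SAE reporting at Week 6.
2. Section 9.2.2: remove the automatic unrelated rule for therapeutic failure, so that relatedness to the reduced dose is assessed case by case.
3. Section 10.3: add all-cause deaths to the findings that prompt an unscheduled DSMB review. The sponsor and DSMB should set the count and its false-alarm rate against a reference rate for the enrolled GCS mix and a stated time horizon. If the charter already has such a rule, restate it here.
4. Synopsis and section 2.6.1: reconcile the two versions of the EFA rule, both the evidence required and the action that follows.

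The cost is protocol wording and a few extra expedited forms: with 50 enrolled, about 50 × 0.081 = 4 to 50 × 0.24 = 12 deaths on the documents' own rates, which differ in population and horizon. The downside is a possible unneeded DSMB call. No extra visits or samples are required.

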9.5 Serious Adverse Event Reporting – Procedures for Investigators

Initial reports

All SAEs occurring from the time of informed consent through 2 weeks within 72 hours of the knowledge of the occurrence (this refers to any adverse event that meets any of the aforementioned serious criteria).

Follow-up reports

The Investigator must continue to follow the patient until the SAE has subsided or until the condition becomes chronic in nature, stabilizes (in the case of persistent impairment), or the patient dies.

Within 24 hours of receipt of follow-up information, the investigator must update the SAE form for the study and submit any supporting documentation (e.g., patient discharge summary or autopsy reports) to the IRB via e-mail. If it is not possible to access the CRF system, refer to the procedures outlined above for initial reporting of SAEs.

9.6 Recording of Adverse Events

Clinical AEs (Grades 3-5) occurring during the first 2 weeks of the research study will be recorded in the CRF, and the Investigator will give his or her opinion as to the relationship of the AE to the study drug treatment (i.e., whether the event is related or unrelated to study drug administration).

All AEs will be documented. A description of the event, including its date of onset and resolution, whether it constitutes an SAE or not, any action taken (e.g., changes to study treatment), and its outcome should be provided, along with the Investigator's assessment

of causality (i.e., the relationship to the study treatment). For an AE to be a suspected treatment-related event, there should be at least a reasonable possibility of a causal relationship between the protocol treatment and the AE. Adverse events will be graded according to *The Division of AIDS (DAIDS) Table for Grading the Severity of Adult and Pediatric Adverse Events (v2.1, July 2017)*.

If the AE is serious, it should be reported immediately to the IRB. Other untoward events occurring in the framework of a clinical study after enrollment are to be recorded as AEs. Laboratory test results do not require individual additional reporting on CRFs as these will be summarized from the statistical database for Grade 1 lab AEs and above.

9.7 Reporting Period for Adverse Events

All AEs regardless of seriousness or relationship to study treatment, spanning from the signing of the informed consent form until 10 weeks are to be recorded on the CRF. The AEs occurring from the signing of the ICF until the first dosing of the study drug will be the pre-treatment AEs. The AEs occurring at or after the first dosing until completion of treatment will be the treatment-emergent AEs (TEAEs). The study will continue with a follow-up period after ~30 calendar days post completion of study drug through 10 weeks.

All AEs resulting in discontinuation from the study should be followed until resolution or stabilization. All new AEs occurring during this period must be reported and followed until resolution unless, in the opinion of the Investigator, the AE or laboratory abnormality/ies is/are not likely to improve because of the underlying disease. In this case, the Investigator must record his or her reasoning for this decision in the patient's medical record.

9.7.1 Laboratory AEs

As laboratory anomalies are common in this population with advanced HIV/AIDS and causality difficult to discern, all laboratory values will be graded but not assigned causality individually.

All lab results shall be reported on 'Blood Results CRF.' Lab abnormalities will be summarized from the statistical database and graded for severity according the DAIDS Toxicity Table. All grades 1-5 will be summarized. These laboratory abnormalities will be summarized separately from clinical AEs.

9.8 Study Medication Discontinuation

This study medicine can be halted or interrupted if the investigator of record has concern of harm by the study drug. If the participant wishes to dose reduce due to intolerance of GI side effects (e.g. nausea), this is allowable. This is not a protocol deviation, but tolerability is an exploratory endpoint. The participant may discontinue the study medicine and remain in the study. Any dose reduction or discontinuation should be recorded on the 'Med CRF' for the study medicine. Before discontinuing the medication, the investigator should consider dividing the scheduled daily dose into smaller doses or dose reduction.

